8.2.2. Key Secondary Efficacy Endpoints

A hierarchical testing strategy to preserve study alpha when testing secondary endpoints was originally planned. The original hierarchical specifications for Part A are retained below for historical perspective. The primary endpoint for Part A is a key secondary endpoint for Part B. Following the change in protocol following the interim analysis, there will be no formal procedure to preserve study-wise type I error. All analyses are descriptive and any findings would need to be confirmed in another study with prospective alpha control.

- First Key Secondary Efficacy Endpoint: Change from baseline (CFB) in log₁₀ SARS-CoV-2 virus RNA
- Second Key Secondary Efficacy Endpoint: Median days to Clinical Recovery (MDCR), from randomization to a disease resolution status in the NIAID Clinical Status scale described in [Section 6.9](#) - i.e. achieving Clinical Status 6, 7, or 8 by Day 14, according to whether the subject is still hospitalized at Day 14 or is an outpatient. Patients without observed clinical recovery will have clinical recovery time assigned as 15 days to preserve the ranks for the comparison
- Third Key Secondary Efficacy Endpoint: Respiratory failure or death

A key secondary efficacy endpoint of the study is the proportion of subjects with Respiratory Failure or Death (RFD), for which the featured assessment will be at Day 28, with additional analyses at Days 10, 14, and 63.

8.2.3. Other Secondary Efficacy Endpoints Secondary endpoints include:

- Change (improvement vs worsening) in the NIAID ordinal scale of overall Clinical Status
- All-cause mortality, to be assessed at all study timepoints, including Days 10, 14, 28, and 63
- Duration of hospitalization/confinement for COVID-19, from start of treatment to achieving Status 6, 7, or 8 on the NIAID Clinical Status scale described in [Section 6.9](#), assessed by time-to-event analyses and by descriptive statistics
- Duration of positive SARS-CoV-2 virus detection in nasopharyngeal/throat swabs, on the schedule indicated in [Table 6-1](#), analysed as time-to-sustained nondetectable SARS-CoV-2 RNA from randomization
- Proportion of subjects who are still SARS-CoV-2 positive at Days 5 and 14 (and longer timepoints as available)

8.2.4. Exploratory Endpoints

Exploratory endpoints include:

- Sparse plasma PK analyses, to assess PK parameters of AT-527 in COVID-19 subjects compared to PK data obtained in healthy human volunteers and HCV patients.
- Time to a National Early Warning Score (NEWS) score ≤ 2 , from Screening/Baseline, for subjects whose Screening NEWS score was >4 (the NEWS score is a patient triaging score developed in Europe)

Protocol Number: AT-03A-001

- Serial assessment of the appearance of antibody to SARS-CoV-2 in study subjects' serum samples, when validated antibody tests become more widely available
- Other relevant COVID-specific tests or SARS-CoV-2 tests that may become available

8.2.5. Safety Endpoints

Safety-related comparisons for the two treatments in this trial will include:

- Proportions of subjects experiencing SAEs
- Proportions of subjects with fatal outcomes
- Proportions of subjects experiencing AEs
 - Overall, and by body system as coded by MedDRA
- Proportions of subjects experiencing drug-attributed AEs
- Proportions of subjects experiencing graded laboratory abnormalities
 - With abnormality grades defined in the referenced DAIDS table
- Proportions of subjects discontinuing study for AEs
- Proportions of subjects discontinuing treatment for AEs

8.3. Efficacy Analysis Methods

8.3.1. Primary Efficacy Analysis

Part A

The ITT population will be the primary efficacy analysis population for Part A. Proportions of subjects (active or placebo-treated) with PRI until study completion (Day 14) will be compared by study arm. The Cochran Mantel Haenszel (CMH) test will be performed to compare the proportion of PRI rate in study arms. Stratification variables will include the randomization strata of geographic regions; additional stratification variables may be described in the eventual SAP, to be finalized prior to database lock.

Part B

Viral load will be assessed quantitatively using a validated assay. The analyses will compare change from baseline log10 viral load at each required scheduled timepoint. The analyses will be carried out on the mITT population. Change from baseline viral load will be compared between the AT-527 group and the placebo group at required post-baseline timepoint using ANCOVA with treatment as a factor and log10 baseline viral load as a covariate. The least squares mean (LSM) change and its standard error of means (SE) in each group, the differences between two groups in LSM change with corresponding 95% confidence intervals (CIs), and p-values will be presented.

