disease progression to successive stages of respiratory insufficiency is potentially lifesaving, as ultimate progression to dependence on intubated respiratory support is associated with a high rate of fatal outcomes (over 50% in U.S. patients, and over 80% in ex-U.S. patients, as noted above).

Additional information for AT-527 can be found in the [AT-527 Investigator's Brochure](#).

Rationale/Background for Amendment 8

[figure not shown]
The clinical development program has been designed on the basis of the emergency nature of the ongoing pandemic. Although the initial primary efficacy goal of the originally designed study was to significantly reduce progressive respiratory insufficiency (PRI), it has become apparent, from blinded analysis, that the background rates of disease progression in this targeted study population are too low to demonstrate clinical efficacy differences between the treatment arms. With a better understanding of the disease resulting in improvements in patient management over time, the disease progression rates observed in this study are much less than the initial assumptions made at the beginning of the study/pandemic, which postulated that 40% of placebo recipients would progress and experience PRI. Due to the low progression rates and in order to support interactions with regulatory agencies, the Sponsor decided to pause enrolment and conduct an interim analysis during the course of the study.

Enrollment in the study was paused after the 81st patient was randomized and the interim analysis (in which the study team remained blinded to individual treatment assignment) was performed on the first 70 patients who completed through Day 14 of the study. Of 62 patients evaluable for the virology analysis, 58 had baseline quantitative viral load data. This interim analysis indicated that AT-527 rapidly reduced viral load levels. At Day 2, patients receiving AT-527 experienced a 0.7 log₁₀ greater mean reduction from baseline viral load as compared to placebo. A sustained difference in viral load reduction was maintained through Day 8 (see figure below). After Day 8, the curves in the groups converge, however, this is expected considering the natural history of the disease in which viral load generally peaks at the time of symptom onset and decreases spontaneously with time.

Protocol Number: AT-03A-001

Quantitative SARS-CoV-2 RNA, mITT (all evaluable patients)
Viral Load **Change from Baseline**

[figure not shown]

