6.1. Medical History

Complete medical history will be obtained at Screening. Information about COVID-19 disease history, including the onset date of symptoms, and risk factors will be collected. Subjects may be questioned about alcohol and drug use, and information about prior or concomitant medications will also be collected.

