Change from baseline viral load at a timepoint will be compared between the AT-527 group and the placebo group ANCOVA with treatment as a factor and \log_{10} baseline viral load as a covariate. In the interim analysis of the first 70 subjects from part A, the observed AT-527 effect at Day 2 was a reduction of 0.7 \log_{10} copies/mL relative to placebo. Assuming a standard deviation for change from baseline of 1.8 \log_{10} copies/mL and 90% of Part B randomized patients eligible for analysis (i.e. 100 patients), there is at least 90% power to detect a true treatment effect of 0.7 at a timepoint using a one-sided test at 0.1 level of significance, not adjusted for multiple comparisons.

Protocol Number: AT-03A-001

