## COVID-19 Statistical Analysis Plan

- Immunoglobulin M (IgM) (if data available);
- Serostatus (positive, negative, indeterminate) (if data available).

The following comorbidities, as captured on the Medical History page of the eCRF, will also be reported for this study:

- Any comorbidity, defined as having any of the comorbidities listed below;
- Diabetes;
- Heart Disease;
- Chronic Lung Disease;
- Chronic Liver Disease;
- Asthma;
- HIV;
- Tuberculosis;
- Alcohol Abuse;
- Drug Abuse.

Continuous demographic and other baseline characteristics will be summarized using descriptive statistics overall and by treatment group based on the SAF analysis set. For categorical demographic and other baseline characteristics, number and percentage of subjects in each category will be provided overall and by treatment group based on the SAF analysis set. No statistical testing will be carried out for demographic or other baseline characteristics.

Demographic, other baseline characteristics, and comorbidities data will be listed.

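### The Part B primary viral-load ANCOVA leaves out time from symptom onset to first dose, a recorded pre-dose covariate, and so may give away a little precision

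*Protocol*

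**What the plan says.** Protocol 8.3.1 sets the Part B primary analysis: change from baseline in log10 viral load in the mITT population, compared "at required post-baseline timepoint using ANCOVA with treatment as a factor and log10 baseline viral load as a covariate". The Synopsis and 8.2.1 give the same model. Baseline viral load is the only covariate.

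The omitted variable is available. Protocol 6.1 states: "Information about COVID-19 disease history, including the onset date of symptoms, and risk factors will be collected". SAP 12.1 derives days from first symptom to Study Day 1, which is the day of first dose (SAP 6.1). The SAP uses illness day as a disease-history descriptor (section 12), as a median-split subgroup that section 16.1.5 applies to PRI (section 7.7), and in a PRI sensitivity analysis that excludes subjects with more than 5 days of symptoms (section 16.1.4). No document puts it in a viral-load model.

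In the Amendment 8 rationale (protocol 1.1), the protocol says that "viral load generally peaks at the time of symptom onset and decreases spontaneously with time". Randomisation is stratified by region only (protocol 8), so illness day is balanced by chance alone.

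**The concern.** If viral load depends on time since onset, two patients with the same measured baseline load but different illness days may have different expected changes, whatever their treatment. Baseline load carries part of this information but need not carry all of it. A single swab is a noisy measure, so of two patients with the same reading, the one later in illness would be expected to have the lower true load.

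Variation that a recorded pre-dose variable could explain would then stay in the residual and widen the interval for the treatment difference. With about 50 patients per arm, precision is scarce. Adjusting for a variable fixed before dosing introduces no systematic bias into a randomised comparison.

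**Working it through.** **Inputs from protocol 8.2.1:** treatment difference 0.7 log10 copies/mL; "Assuming a standard deviation for change from baseline of 1.8" log10 copies/mL; 100 analysable patients, 50 per arm at 1:1; test "using a one-sided test at 0.1 level of significance". The claim is that "there is at least 90% power to detect a true treatment effect of 0.7".

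**Input not in the documents:** the partial R² of illness day for change in viral load, given baseline load. A range of 0.01 to 0.10 is assumed.

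**Step 1, the plan's own figure.** SE = 1.8 × √(2/50) = 0.360. Power = Φ(0.7/0.360 − 1.282) = Φ(0.663) = 74.6% (74.4% with the noncentral t). The stated 90% is not reproduced. Reaching it with 50 per arm needs a residual SD of 0.7 / [(1.282 + 1.282) × 0.2] = 1.366, which the protocol does not state.

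**Step 2, adding illness day.** The SE is multiplied by √(1 − R²). Taking 1.8 as the residual SD:

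| Assumed partial R² | SE | Fall in SE | Power |
|---|---|---|---|
| 0 | 0.360 | none | 74.6% |
| 0.01 | 0.358 | 0.5% | 74.9% |
| 0.05 | 0.351 | 2.5% | 76.2% |
| 0.10 | 0.342 | 5.1% | 77.9% |

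The largest gain is 77.9 − 74.6 = 3.3 points. For illness day alone to reach 90%, its partial R² would have to be 1 − (1.366/1.8)² = 0.42.

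**Step 3, if baseline adjustment already brings the residual SD to 1.366.** Power at R² of 0, 0.01, 0.05 and 0.10 is 90.0%, 90.2%, 91.1% and 92.2%. The proportional fall in SE is the same; the gain in power is smaller.

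**Step 4, is the assumed range reasonable?** Onset must fall within 5 days before Screening, and dosing should start within 24 hours of confirmed eligibility, so illness day spans about 5 to 6 days. If it is uniform (assumed), its SD is 5/√12 = 1.44 to 6/√12 = 1.73 days. With an assumed slope of 0.1 to 0.3 log10 per day on the change score, given baseline load, R² = (slope × SD / 1.8)² runs from (0.1 × 1.44 / 1.8)² = 0.006 to (0.3 × 1.73 / 1.8)² = 0.083. So 0.10 is already a little generous.

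**Step 5, the charge for the extra term.** Chance correlation between illness day and arm inflates the variance of the contrast by roughly 1/(100 − 1), about 1%. Step 2 leaves this out, so the gain at R² = 0.01 is close to nil.

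**The case against.** The strongest objection is that a loss of precision has not been shown. No section reports how illness day relates to change in viral load once baseline load is in the model. If every patient declined at the same steady rate and baseline load were measured without error, illness day would add nothing. The eligibility window also limits its spread. This stands as to size: every R² above is an assumption. It does not remove the case for the covariate, because baseline load is measured with error and the term costs almost nothing.

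Baseline-adjusted ANCOVA is a valid analysis, and a further prognostic covariate is optional. That also stands; this is an improvement, not an error.

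The consequence is limited. Protocol 8.2.1 makes the Part B p-values descriptive, and the March 2022 Changes to Planned Statistical Analyses Form restricts Part B output to listings.

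Three stronger readings are tempting, and the documents do not support them:

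- A reader might take the natural-history sentence in protocol 1.1 to mean that illness day governs the change in viral load, or that patients enrolled early are still on a rising curve. The sentence explains why the curves converge after Day 8. It places the peak at symptom onset, so enrolled patients, already symptomatic, would be at or past it.
- A reader might multiply a daily rate of decline by a chance difference between arms in illness day and read the product as bias against the 0.7 target. That product is a shift in viral-load level. The endpoint is change adjusted for baseline, so the baseline covariate absorbs most of it.
- A reader might want serostatus added as well. The SAP lists it only if data are available (section 10), and protocol section 6 lets sites skip the stored samples, so it cannot be relied on as a primary-model covariate.

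**Conclusion.** The point holds as a modest, nearly free improvement. The Part B primary model omits a recorded pre-dose variable that the protocol itself links to viral load, and this may give away some precision. On an assumed partial R² of 0.01 to 0.10 the SE would be about 0.5% to 5% lower, worth at most about 3 points of power. Confidence in the omission is high; the size rests wholly on the assumed R² and, for the absolute figures, on reading 1.8 as the residual SD.

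The treatment estimate remains valid without the covariate. Nor should the change be offered as a remedy for the power statement: the shortfall from 90% to about 75% is a separate and larger matter, which this leaves open under any R² in the assumed range.

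**What to change.** In protocol 8.3.1, and in the matching text of the Synopsis and 8.2.1, add days from symptom onset to first dose as a continuous covariate beside log10 baseline viral load. Keep the baseline-only ANCOVA as a sensitivity analysis, and state how a missing onset date would be handled.

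Put the same model in a Part B section of the SAP. SAP v1.0 describes only the 550 mg study, so amending its section 16.2.4.1 would not cover Part B.

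The cost is a short wording change in each document, one degree of freedom and no new data collection. It matters only if Part B is analysed rather than listed. The Part A viral-load ANCOVA is still tabulated under the March 2022 form; any version of it adjusted for illness day that is added now should be labelled post hoc.

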8. STATISTICAL ANALYSES

This section summarizes the statistical analyses pertinent to the efficacy and safety assessments in this study. A statistical analysis plan (SAP) describing the detailed statistical methods for this study will be prepared and finalized before database lock. Sample size calculations and power

Protocol Number: AT-03A-001

statements, with the exception of those for time to Clinical Recovery, were performed using SAS/STAT v9.4 (SAS Institute Inc., Cary, NC, USA). The power estimates for time to Clinical Recovery were computed by simulation. Corresponding code is provided in [Section 13](#).

All analyses of trial data will be performed in this version of SAS/STAT or higher unless noted in the eventual SAP that other software will be utilized.

This is a double-blind randomized study, with variable size block randomization stratified by region.

In order to support interactions with regulatory agencies, the Sponsor may choose to conduct interim analyses during the course of the study. The decision to conduct an interim analysis and the timing of the analysis will be documented in the Sponsor's trial master file prior to the conduct of the interim analysis. The interim analysis will be performed and interpreted by members of the Sponsor study team and appropriate senior management personnel, who will be unblinded at the treatment group level.

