8.3.2. Key Secondary Analyses

Change from baseline in amount of quantitative viral load (Part A only)

Viral load will be assessed quantitatively using a validated assay. The analyses will compare change from baseline log10 viral load at each required scheduled timepoint. Only patients with measurable viral load at baseline will be included in the analyses. Change from baseline viral load will be compared between the AT-527 group and the placebo group at each of Days 2, 5, and 14 using ANCOVA with treatment as a factor and log10 baseline viral load as a covariate. The least

Protocol Number: AT-03A-001

squares mean (LSM) change and its standard error of means (SE) in each group, the differences between two groups in LSM change with corresponding 95% confidence intervals (CIs), and p-values will be presented. Statistical significance will be tested at Day 5, which is a time point with required sample collection in all versions of the protocol, using on one-sided 0.025 level test. If statistical significance is observed at Day 5, then Day 2 would also be tested. The Day 14 comparison will be descriptive. Descriptive summaries and comparisons at non-required timepoints may also be presented.

Median Days to Clinical Recovery

The Wilcoxon Mann-Whitney test will be utilized for the first key secondary endpoint analysis because the distribution of days until clinical recovery is not anticipated to be normally distributed.

Proportion of Subjects with Respiratory Failure or Death

This secondary endpoint will be analyzed in the same fashion as the primary endpoint, as it is similarly a proportion analysis.

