## 7.6. ADJUSTMENTS FOR COVARIATES AND FACTORS TO BE INCLUDED IN ANALYSES

The analyses will be adjusted for the following covariates and factors.

- Geographic regions (stratification variable for randomization)
  - North America
  - South America
  - Europe
  - Rest of World
- Baseline quantitative SARS-CoV-2 (virologic endpoints only)

If data are too sparse for one level of the Geographic region factor (i.e., less than 5% of subjects), South America and Rest of World will be combined. If the level is still less than 5% of subjects, then the factor will not be included in the statistical model/test. Determination of the factor(s) to be included into the statistical models/tests will be finalized before the study DBL in a blinded fashion.

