The analyses will compare change from baseline log10 quantitative SARS-CoV-2 at each required scheduled timepoint. Any missing data will not be included in the analyses. Change from baseline quantitative SARS-CoV-2 will be compared between the AT-527 group and the placebo group at each of days 2, 5, and 14 using ANCOVA with treatment as a factor and log10 baseline quantitative SARS-CoV-2 as a covariate. For each time point and LOQ handling method, the least squares mean (LSM) change and its standard error of means (SE) in each group, the differences between two groups in LSM change with corresponding 95% confidence intervals (CIs), and p-values will be presented. Statistical significance at Day 2 and Day 5 will be assessed based on two-sided 0.025 level test to account for 2 comparisons. The formal statistical comparison will be based on Method 1.

The raw and LSMs change from baseline in log10 will also be presented graphically over time.

#### 16.2.4.2. Time to Clinical Recovery (days) by Day 14

Another key secondary efficacy goal is to shorten the median days to clinical recovery (MDCR) by at least 4 days for active-dosed subjects compared to placebo recipients during the 14-day primary study period. The median times

Document: \[REDACTED]\net\enterprise\Apps\sasdata\SASb\SAS\Atea\_Pharmaceuticals\AT-527\5ZA63631\Biostatistics\Documentation\SAP\AT-03A-001\_V1.0\_COVID\_SAP\_PA7.doc  
Author: \[REDACTED] Version Number: V1.0  
Template No.: CS\_TP\_BS016 Revision 6 Version Date: 15Apr2021  
Effective Date: 02Dec2019 Reference: CS\_WI\_BS005

Copyright © 2009, 2010, 2012, 2016, 2018, 2019 \[REDACTED] All rights reserved. The contents of this document are confidential and proprietary to \[REDACTED] Holdings Inc. and its subsidiaries. Unauthorized use, disclosure or reproduction is strictly prohibited.

to clinical recovery will be presented for each treatment group as well as the number and percentage of subjects with and without clinical recovery. The Wilcoxon Mann-Whitney test will be used to test that there is no difference between the treatment groups by a one-sided  $\alpha=0.025$  p-value.

As a sensitivity analysis a Kaplan-Meier curves (product-limit estimate) will be provided by treatment arm for the time to clinical recovery (days). Subjects will be censored as follows:

- If subject dies without clinical recovery, censor at Day 15
- If subject has no post-baseline scale, censor at Day 1

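### The viral-load ANCOVA leaves out region, the only randomisation stratum: for Part A this conflicts with SAP 7.6, for Part B it is unexplained, and the cost is nil to modest depending on how far region predicts viral-load change

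*Protocol*

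**What the plan says.** Protocol section 8 describes "variable size block randomization stratified by region"; no other stratification factor is named.

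The viral-load model is stated several times, always with the same two terms:

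- Protocol 8.3.1 (Part B primary): "ANCOVA with treatment as a factor and log10 baseline viral load as a covariate". The synopsis and protocol 8.2.1 give the same model.
- Protocol 8.3.2 (Part A first key secondary): "using ANCOVA with treatment as a factor and log10 baseline viral load as a covariate".
- SAP 16.2.4.1 (Part A): "ANCOVA with treatment as a factor and log10 baseline quantitative SARS-CoV-2 as a covariate".

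SAP 7.6 sets a general rule: "The analyses will be adjusted for the following covariates and factors". Its list opens with "Geographic regions (stratification variable for randomization"), which carries no restriction by endpoint and has four levels. The second item is "Baseline quantitative SARS-CoV-2 (virologic endpoints only"). SAP 7.6 also says that South America and Rest of World are combined if a level holds fewer than 5% of subjects, that region is dropped if the level is still that small, and that this is settled blinded before database lock.

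Elsewhere the plan does control for region: in the CMH test for PRI (protocol 8.3.1, SAP 16.1.3), for respiratory failure or death (SAP 16.2.4.3, by reference), and for the proportion still SARS-CoV-2 positive (SAP 16.2.5), which is itself a virologic endpoint.

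**The concern.** In SAP 7.6 the restriction to virologic endpoints attaches only to baseline viral load. Read plainly, a virologic analysis carries both region and baseline. SAP 16.2.4.1 then writes a model with baseline alone. A programmer who follows one section and a programmer who follows the other would report different estimates, standard errors and p-values for Part A. The changes form of March 2022 alters the display of the ANCOVA results but does not settle the model.

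There is also a statistical reason to include the stratum. Blocking within region balances the arms within region, which removes between-region variation from the treatment difference. A model without region still counts that variation as residual error. If region is prognostic, the estimated standard error is then larger than the true one, the confidence interval is too wide and the test rejects too rarely.

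At stake are the primary analysis of a part that the protocol calls signal seeking, and the first key secondary comparison of Part A. The possible loss is precision. Treatment-effect bias and an inflated false-positive rate are not at issue.

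**Working it through.** **Inputs (protocol 8.2.1, Part B).** Difference 0.7 log10, SD 1.8 log10, 100 analysable patients at 1:1 (50 per arm), one-sided level 0.1, stated power at least 90%.

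**The plan's own figure.**

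- SE = 1.8 × √(2/50) = 0.360
- Power = Φ(0.7/0.360 − 1.2816) = Φ(0.663) = 74.6%; the noncentral t gives 74.4%

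The stated 90% does not reproduce. It would need 87 per arm. Reading the 100 patients as per arm gives 92.9%, which may explain the figure. This is a separate problem; 74.6% is simply the starting point below.

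**Effect of region.** Let R² be the share of the two-term model's residual variance that region explains. The documents give no value, so a range is assumed. The SD of 1.8 is treated as the residual SD of the two-term model.

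- True SE under blocks within region, for either model: 0.360 × √(1−R²)
- SE that the two-term model reports: 0.360
- Power with region: Φ(0.7 / [0.360√(1−R²)] − 1.2816)
- Power without region: Φ((0.7/0.360 − 1.2816) / √(1−R²))
- Actual size without region: 1 − Φ(1.2816 / √(1−R²))

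| R² | True SE | Power without region | Power with region | Gain (points) | Actual size without region (nominal 0.1) |
|---|---|---|---|---|---|
| 0 | 0.360 | 74.6% | 74.6% | 0 | 0.100 |
| 0.05 | 0.351 | 75.2% | 76.2% | 1.0 | 0.094 |
| 0.10 | 0.342 | 75.8% | 77.9% | 2.1 | 0.088 |
| 0.15 | 0.332 | 76.4% | 79.6% | 3.2 | 0.082 |
| 0.20 | 0.322 | 77.1% | 81.4% | 4.3 | 0.076 |
| 0.25 | 0.312 | 77.8% | 83.2% | 5.4 | 0.069 |

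Power without region also rises with R², because stratified blocking shrinks the true SE whichever model is fitted. The gain must therefore be taken between the two columns at the same R², not against a fixed 74.6%.

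A simulation with four near-equal regions (8,000 runs) agrees: 74.0% against 74.0% at R² = 0, 74.8% against 77.0% at 0.10, and 76.4% against 80.6% at 0.20.

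**Cost if region explains nothing.** Region takes at most 3 degrees of freedom of the 97 left by the two-term model. The noncentral t with region fitted gives 74.4% at R² = 0. That is about 0.2 points below the normal approximation, and nearly all of this is the approximation itself, since the t calculation without region also gives 74.4%.

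**Part A as planned** (SAP 7.1: difference 1, SD 2, 90% of 182 so about 82 per arm, two-sided 0.05). Power is 89.3%, consistent with the stated minimum of 85%. Without against with region it is 90.5% against 92.1% at R² = 0.10, and 91.7% against 94.7% at R² = 0.20. Part A stopped at 81 randomised, so these figures describe the plan and not the sample obtained.

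**The case against.** The strongest reply is that this is a matter of wording with little behind it. Four parts of that case deserve an answer.

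- **No evidence that region matters.** This stands. No document quantifies a regional effect on viral load. Protocol 1.1 says that standard of care will vary by country, but the strata are four broad regions, other agents with possible SARS-CoV-2 activity are prohibited at every site (protocol 5.8.3), and results come from a central laboratory. A reader might infer that the standard errors are in fact too wide and that power is in fact lost. The documents do not support that; both statements are conditional.
- **The SAP does not govern Part B.** This stands. SAP version 1.0 describes only the 550 mg design, and the changes form says that the SAP will not be updated and that Part B patients will only be listed. A reader might infer that the Part B primary analysis breaches SAP 7.6; it does not, because that section was not written for it.
- **The stakes are low.** This largely stands. Protocol 8.2.1 calls the Part B p-values descriptive, protocol 8.2.2 keeps the Part A hierarchy for history only, and any error is conservative.
- **SAP 7.6 already deals with it.** This stands only in part. The sparse-region rule could remove region after a blinded review, but SAP 16.2.4.1 does not invoke it. If SAP 7.6 prevails, region is already in the Part A model; if SAP 16.2.4.1 prevails, it is not. The SAP does not say which prevails, and it gives no reason to adjust SARS-CoV-2 positivity for region but not viral load.

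**Conclusion.** The point holds in a limited form. Region is the only randomisation stratum and is absent from every statement of the viral-load ANCOVA. For Part A, SAP 7.6 and SAP 16.2.4.1 specify different models and must be reconciled. For Part B, the omission is an unexplained choice in a descriptive primary analysis.

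The size depends on an assumption. With R² for region between 0 and 0.25, adding region to the Part B model gains between nothing and about 5 points of power, and the nominal 0.1 test without region has an actual size between 0.100 and about 0.07. At R² of 0.05 to 0.10 the gain is only 1 to 2 points. These figures rest on balanced blocks within region, 50 analysable patients per arm, and 1.8 as the residual SD.

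A reader might hope that adjusting for region would restore the 90% power claimed in protocol 8.2.1. That would need an R² of about 0.42, and nothing in the documents suggests one. The shortfall from 90% to about 75% is a separate matter. The case for change rests mainly on the Part A inconsistency and on analysing the trial as it was randomised; the power gain is secondary.

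**What to change.** In the synopsis, protocol 8.2.1, 8.3.1 and 8.3.2, and SAP 16.2.4.1, state the model as ANCOVA with treatment and randomisation region as factors and log10 baseline viral load as a covariate. Refer to the SAP 7.6 rule for pooling or dropping sparse regions, decided blinded before database lock. Keep the two-term model as a sensitivity analysis. If the sponsor prefers the two-term model, give the reason and amend SAP 7.6 to exempt the viral-load ANCOVA.

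The cost is one line in each place, one class variable in the program, and at most 3 degrees of freedom. Correct the Part B power statement separately.
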